# 9.1 General Specifications and Definitions for Analysis

#### Pooling of centers

Data will be pooled across centers.

# Data handling after interim analysis cut-off date

Data after the cut-off date may not undergo the cleaning process and will not be displayed in any listings or used for summary statistics, statistical analyses, or imputations. For example, laboratory values of samples taken after data cut-off, adverse events (AEs) with onset date after data cut-off, etc. will not be included in any analysis or listing. Stop dates, however, are not affected by this rule – e.g. if an AE starts prior to the cut-off, but stops after date of cut-off, the AE end date will be included in listings.

## Presentation of continuous and qualitative variables

Continuous variables will be summarized using descriptive statistics i.e., number of subjects considered and number of missing values, [i.e., n (missing)], mean, median, standard deviation (StDev), minimum, maximum and first and third quartile (Q1 and Q3). As per general reporting conventions, mean, median, Q1, and Q3 will be displayed with one more decimal place than the raw data; StDev will be displayed using two more decimal places than the raw data. Percentages will be reported to one decimal place. Rounding will be performed to closest integer/decimal using the common mid-point between the two consecutive values – e.g., 5.1 to 5.4 will be rounded to an integer of 5, and 5.5 to 5.9 will be rounded to an integer of 6.

Qualitative variables will be summarized by frequency counts and percentages. Unless otherwise stated, the calculation of proportions/percentages for a given qualitative variable will include subjects with missing values in the denominator. When applicable, counts of missing observations for a qualitative variable will be presented on summary tables.

Unless otherwise specified, percentages will be based on the number of subjects in the analysis set used for the given summary.

For presentation of PK results please refer to Section 9.2.

#### Definition of baseline

In general, the last non-missing measurement prior to the first study intervention will serve as the baseline measurement. Study intervention includes avelumab, M3814, and in the case of participants in Part B, RT. If the time of an assessment and/or the time of the initial dosing are unknown and dosing date and assessment date are the same, the following rule is used: assessments intended to be completed prior to dosing, as per protocol, and completed on scheduled visits are assumed to have been performed prior to dosing and may be selected as baseline; assessments completed on unscheduled visits are assumed to have been performed after dosing and are not eligible for selection as baseline. Unscheduled assessments which occur unambiguously prior to the start of any study intervention are eligible for selection as baseline.

### Definition of change from baseline

Change from baseline = visit value - baseline value

Percent Change from Baseline = 100 \* (visit value – baseline value) / baseline value

#### Significance level

All statistical tests mentioned in this IAP are to be regarded as exploratory. If confidence intervals (CIs) are to be calculated, these will be two-sided with a confidence probability of 95%, unless otherwise specified in this IAP.

#### Conversion factors

The following conversion factors will be used to convert days into months or years:

1 month = 30.4375 days, 1 year = 365.25 days.

Details for determination of participant age and body mass index (BMI) are given in Section 11.1.

#### Definition of duration

Duration will be calculated by the difference of start and stop date + 1. For example, AE duration (days) = AE end date - AE start date + 1

Unless otherwise specified, the time since an event will be calculated as reference date minus date of event. For example, time since last dose date will be calculated as the event date – the date of last dose.

## Definition of treatment day

Treatment day is defined relative to the date of first dose of any study intervention. Study intervention includes avelumab, M3814, and in the case of participants in Part B, RT. Day 1 represents the first day of treatment, the day before is defined as Day -1 (no Day 0 is defined).

### Definition of on-treatment period

The on-treatment period is defined as the time from the first dose of study treatment through the minimum of (last date of study intervention + 30 days, start day of new anti-cancer drug therapy - 1 day, death).

#### Scheduled and unscheduled visits

Assessments from unscheduled visits will be considered for the derivation of baseline values and worst on-treatment values and grades; they will also be included in listings. Please see Section 9.3 for details on visit windowing.

#### Software

All analyses will be performed using SAS® Software version 9.4 or higher, with the exception of M3814 and M467 PK parameters which will be derived using noncompartmental methods with the validated computer program Phoenix® WinNonlin® 8.0 or higher (Certara, L.P., Princeton, New Jersey, USA).

#### 9.2 Presentation of Pharmacokinetic Results

### 9.2.1 Presentation of Pharmacokinetic Concentration Data

M3814,  $\theta$ -demethylated product M467 (if available), and avelumab concentration data will be descriptively summarized using: number of non-missing observations (n), arithmetic mean (Mean), standard deviation (StDev), coefficient of variation (CV%), minimum (Min), median (Median) and maximum (Max). In cases with  $n \le 2$ , only n, Min, and Max will be reported.

Descriptive statistics of PK concentration data will be calculated using values with the same precision as the source data and rounded for reporting purposes only. The following conventions will be applied when reporting descriptive statistics of PK concentration data:

Mean, Min, Median, Max: 3 significant digits
StDev: 4 significant digits
CV%: 1 decimal place

# 9.2.2 Presentation of Pharmacokinetic Parameter Data

Pharmacokinetic parameter data will be descriptively summarized using: n, Mean, StDev, CV%, Min, Median, Max, geometric mean (GeoMean), and the geometric coefficient of variation (GeoCV). For time to reach maximum observed concentration ( $t_{max}$ ), only n, Min, Median, and Max will be reported. In cases with  $n \le 2$ , only n, Min, and Max will be reported. The PK parameter maximum observed plasma concentration ( $t_{max}$ ) will be reported with the same precision as the source data. All other PK parameters will be reported to 3 significant figures. In export datasets, as well as in the SDTM PP domain, PK parameters will be provided with full precision, and will

CONFIDENTIAL

not be rounded. Descriptive statistics of PK parameter data will be calculated using full precision values and rounded for reporting purposes only.

The following conventions will be applied when reporting descriptive statistics of PK parameter data:

Mean, Min, Median, Max, GeoMean: 3 Significant digits StDev: 4 Significant digits CV%, GeoCV%: 1 decimal place

#### 9.2.3 Visit Windowing

The assignment of visit windows is described in Table 2 and Table 3 for Part A and Part FE subjects, and Table 4 and Table 5 for Part B subjects for the purpose of by-visit analyses of laboratory assessments, vital signs (VS), and electrocardiogram (ECG) data. In addition to those tables, the following rules will be used for assignment of visits:

- Baseline will be derived as described in Section 9.1.
- Both scheduled and unscheduled assessments are considered in visit windowing.
- No visit windowing will be performed at End-of-Treatment, Safety Follow-up, or Long-Term Follow-up visits. Instead, the earliest non-missing observation among the unscheduled or scheduled assessments for each visit will be used.
- If there are multiple assessments for any specified visit and some of them are from scheduled visits with non-missing assessment results, the assessment from scheduled visit that is closest to the planned study day will be used for analysis. If two scheduled visits are equally spaced around the assigned study day, the earlier of the two will be used.
- If there are multiple assessments for any specified visit and none of them are from scheduled visits, the assessment with non-missing results and closest to the planned study day will be used
- If there are two or more unscheduled assessments with non-missing results and the same distance to the planned study day, the assessment prior to the planned study day will be used in deriving visit window. For example, if the lab assessment was done on both Study Day -1 and 1, then the assessment on Study Day -1 will be used for visit windowing.

Table 2: Visit Window Definition for Lab Assessments for Part A & FE Participants

Assigned Study Day (Inclusive)		Planned Study	Analysis Visit	
From (AWLO)	To (AWHI)	Day (AWTARGET)	(N) (AVISITN)	Analysis Visit (AVISIT)
-28	-1	-1	100	Screening
~	1		1	Baseline
1	4	1	101	Visit 1 Day 1
5	25	22	103	Visit 3 Day 22
26	32	29	104	Visit 4 Day 29
33	60	57	106	Visit 6 Day 57
61	88	85	108	Visit 8 Day 85
Further lab visits are scheduled for even visit numbers (X = 12, 14,), and the following algorithm can be applied:				
Y-24	Y+3	Y = (X-2) * 14 + 1	100+X	Visit X Day Y

Table 3: Visit Window Definition for Vital Sign & ECG Assessments for Part A & FE **Participants** 

Assigned Study Day (Inclusive)		Blanced Study	Amelica Vicio	
From (AWLO)	To (AWHI)	Planned Study Day (AWTARGET)	Analysis Visit (N) (AVISITN)	Analysis Visit (AVISIT)
-28	-1	-1	100	Screening*
~	1		1	Baseline*
1	4	1	101	Visit 1 Day 1*
5	18	15	102	Visit 2 Day 15*
19	25	22	103	Visit 3 Day 22*
26	32	29	104	Visit 4 Day 29
33	46	43	105	Visit 5 Day 43
47	60	57	106	Visit 6 Day 57
61	74	71	107	Visit 7 Day 71
75	88	85	108	Visit 8 Day 85
* Visit also includes ECG assessment.  Further vital sign assessments are scheduled at each biweekly visit, and the following algorithm can be applied:				
Y-10	Y+3	Y = (X-2) * 14 + 1	100+X	Visit X Day Y

Table 4: Visit Window Definition for Lab Assessments for Part B Participants

Assigned Study Day (Inclusive)		Planned Study	Analysis Visit	
From (AWLO)	To (AWHI)	Day (AWTARGET)	(N) (AVISITN)	Analysis Visit (AVISIT)
-35	-1	-1	100	Screening
~	1		1	Baseline
1	1	1	202	Part B Visit 2 Day 1
2	7	5	206	Part B Visit 6 Day 5
8	15	12	211	Part B Visit 11 Day 12
16	43	29	213	Part B Visit 13 Day 29

Table 5: Visit Window Definition for Vital Sign & ECG Assessments for Part B Participants

Assigned Study Day (Inclusive)		Blanned Study	Analysis Visit	
From (AWLO)	To (AWHI)	Planned Study Day (AWTARGET)	Analysis Visit (N) (AVISITN)	Analysis Visit (AVISIT)
-35	-1	-1	200	Screening
~	1		1	Baseline
1	1	1	202	Part B Visit 2 Day 1*
2	2	2	203	Part B Visit 3 Day 2
3	3	3	204	Part B Visit 4 Day 3
4	4	4	205	Part B Visit 5 Day 4
5	5	5	206	Part B Visit 6 Day 5
8	8	8	207	Part B Visit 7 Day 8
9	9	9	208	Part B Visit 8 Day 9
10	10	10	209	Part B Visit 9 Day 10
11	11	11	210	Part B Visit 10 Day 11
12	13	12	211	Part B Visit 11 Day 12
14	16	15	212	Part B Visit 12 Day 15
17	30	29	213	Part B Visit 13 Day 29*
* Visit also includes ECG assessment.				

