Physical Exam (PE)	х	x		x			Perform at Visit 6 (Week 8) and then Q8W	x	x			Complete PE at Screening (can be up to 28 days prior to the first study interventions), Day 1 prior to the first administration of study interventions, and Day 22. A PE only required at EoT if participant has not started a new antitumor treatment. Symptom-oriented PE at each visit if deemed necessary by the Investigator.
ECOG Performance Status	X		x	X	X	X	x	X	X			
AE Assessment	x	x	x	x	x	x	х	x	x	x	х	Continuously, at EoT, and Safety FU, ongoing treatment-emergent AEs should be evaluated. At Long-term FU, only needed if participant has not started a new antitumor treatment.
Concomitant Medications	X	X	X	X	X	X	X	X	X	X	X	

	Treatment Period: M3814+aveluma				avelumab	End	of Trea	tment	(EoT)/FU	Notes		
Study Period	Screening	DL	T Peri	od				EoT	Safet	ty FU	Long-term FU	
Visit	-1	1	2	3	4	5	n				Q12W	During on-treatment period, after Day 29, visits
Study Day (± Visit window)	-28 to -1	1	15 (± 1)	22 (± 1)	29 (± 1)		n + 14 d (± 2)	(Within 7 days of decision to disconti nue)	(± 5)	90 d (± 5)	(± 7)	will be every 2 wks on days of avelumab infusions until EoT. All participants discontinuing study interventions for any reason must undergo EoT Visit within 7 days after decision to discontinue study interventions, but (if possible) before any new antineoplastic therapy is started. The safety follow-up period will be 30 days (± 5 days) after the last dose of avelumab, see Section 4.1.1.3.
M3814		Cont	inuou	s BID	dosi	ing (7	days/wk)					See Section 6.6.5.1 for details.
Premedication (avelumab)		X	x		X	x						Required only for first 4 avelumab infusions, as needed thereafter. See Section 6.5.5.
Avelumab		x	x		x	x	x					800 mg iv Q2W until PD. For post-PD treatment, see Section 6.6.6. For post-CR treatment, see Section 4.1.1.2.
Hematology, Serum Chemistry	x	x		x	x		Q4W	x	×			Baseline complete hematology and core serum chemistry analyses could be performed within the Screening period (can be up to 28 days prior to the first administration of study interventions). Prior to the administration of study interventions, the most recent complete hematology and core serum chemistry results must be available and reviewed. See Appendix 6.

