# 15.3.1 Hematology and Clinical Chemistry Parameters

All statistical analyses of laboratory values will be performed using SI units.

Any subject with an abnormal hematology or chemistry result will have all records for the parameter with the abnormal result included in a listing. Pertinent details, including value, change from baseline, normal range indicator, and toxicity grade (where applicable) will be provided.

Quantitative data will be examined for trends in actual values and the change from baseline through presentation of boxplots shown over time, at each visit. In addition, a boxplot of the change from baseline to the worst on-treatment record for each parameter will be produced.

Listings will include all the hematology and chemistry laboratory parameters as available in the database with the all corresponding relevant information.

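### SAP Table 2 has no laboratory window for Visit 10, so on-schedule Day 113 labs in Parts A and FE belong to no analysis visit

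*SAP*

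**What the plan says.** SAP Section 9.2.3 assigns visit windows "for the purpose of by-visit analyses of laboratory assessments, vital signs (VS), and electrocardiogram (ECG) data". Table 2 covers laboratory assessments in Parts A and FE. Its last explicit row is "61 88 85 108 Visit 8 Day 85": from Day 61 to Day 88, target Day 85, analysis visit number 108. Below that row the table continues by rule: "Further lab visits are scheduled for even visit numbers (X = 12, 14", and so on. The planned day is Y = (X-2)*14+1, and the window runs from Y-24 to Y+3 inclusive.

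On the protocol side, the Schedule of Activities (Section 1.3, Table 1 for Part A and Table 4 for Part FE) carries the row "Hematology, Serum Chemistry x x x x Q4W". The notes to the same tables say that after Day 29 visits "will be every 2 wks on days of avelumab infusions until EoT", and the column for these later visits allows ± 2 days.

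The windows feed SAP Section 15.3.1, which examines actual values and change from baseline by "presentation of boxplots shown over time, at each visit".

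**The concern.** The explicit rows stop at Visit 8 and the formula begins at Visit 12. Visit 10 is even-numbered and is a scheduled laboratory day, but it has neither a row nor a place in the list. If the specification is followed literally, results from that visit receive no analysis visit and drop out of any display organised by visit.

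At stake is one complete scheduled time point, 16 weeks after Day 1, in the laboratory trend plots. Cohorts have 3 to 6 participants per dose level and numbers fall as participants leave treatment, so each late time point matters for reading a trend. A reader of the plots would see nothing between Day 85 and Day 141 and could not tell whether labs were missing or had not been mapped.

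**Working it through.** **Inputs**

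- Window rule: Y = (X-2)*14+1, window [Y-24, Y+3], from X = 12 in steps of 2 (SAP Table 2).
- Last explicit row: Visit 8, Day 85, Days 61 to 88 (SAP Table 2).
- Laboratory frequency after Day 29: every 4 weeks in Parts A and FE (Protocol Tables 1 and 4).
- Visit spacing after Day 29: every 2 weeks, ± 2 days (same tables).

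**Step 1. Reproduce the plan's own rows.** The formula is tested on two visits that the table lists explicitly.

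- X = 6: Y = 4*14+1 = 57; window 57-24 = 33 to 57+3 = 60. Table 2 has Day 57, Days 33 to 60.
- X = 8: Y = 6*14+1 = 85; window 61 to 88. Table 2 has Day 85, Days 61 to 88.

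Both match exactly, so the explicit rows and the formula describe one scheme.

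**Step 2. Apply the rule as written.**

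| X | Planned day Y | Window | Covered by Table 2 as written? |
|---|---|---|---|
| 8 | 85 | 61 to 88 | Yes, explicit row |
| 10 | 8*14+1 = 113 | 89 to 116 | No |
| 12 | 10*14+1 = 141 | 117 to 144 | Yes, by formula |
| 14 | 12*14+1 = 169 | 145 to 172 | Yes, by formula |

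The gap runs from Day 89 to Day 116: 116-89+1 = 28 days. Mapping every study day from 1 to 399 to the table gives the same result: these 28 days are unassigned, every other day is assigned, and no day is assigned twice.

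**Step 3. Compare with the protocol schedule.** Four-weekly labs counted from Day 29 fall on Days 57, 85, 113 and 141. Two-weekly visits from Visit 4 (Day 29) put Visit 10 at 29+6*14 = Day 113. With ± 2 days around that planned day, Visit 10 falls on Days 111 to 115, entirely inside the gap.

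**Step 4. Compare with the sister table.** SAP Table 3 (vital signs and ECG, same study parts) also ends its explicit rows at Visit 8, but its rule continues at each two-weekly visit with window [Y-10, Y+3]. Visit 9 gets Days 89 to 102 and Visit 10 gets Days 103 to 116, with no gap. At the same Visit 10, vital signs would therefore be mapped and labs would not.

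**Step 5. Start the rule at X = 10.** Visit 10 takes Days 89 to 116. Repeating the day-by-day mapping over Days 1 to 399 leaves no unassigned day and creates no overlap.

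**The case against.** Four points can be made on the other side.

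- **The intended rule can be recovered.** The sentence speaks of even visit numbers, Visit 10 is even, and the printed formula gives the right window for it. A careful programmer might notice scheduled records without a visit and fill the gap. That is true, but doing so means departing from the visit list that the SAP states.
- **The numeral could be a PDF-reading fault.** The ellipsis that should follow 14 appears to have been lost in the PDF text, so a lost 10 cannot be strictly excluded. Nothing positive points to it, however: the list opens cleanly at 12, and the printed formula reproduces the Visit 6 and Visit 8 windows exactly. A look at the source file settles it.
- **Not every Visit 10 result is necessarily lost.** A visit delayed to Day 117 or later falls into the Visit 12 window, and labs from an end-of-treatment visit on Days 89 to 116 are kept because that visit is not windowed. This is correct, but such results would not appear under Visit 10 either, because the displays have no Visit 10.
- **The reach is narrow.** The by-visit laboratory output that the SAP names is the set of boxplots over time. Worst-grade tables, shift tables, liver summaries, listings and the baseline-to-worst boxplot do not use these windows, and all analyses are exploratory. This stands, and it limits the weight of the point.

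**Conclusion.** The point holds. As written, Table 2 leaves Days 89 to 116 (28 days) without a laboratory analysis visit, and every Visit 10 hematology and chemistry result taken within the protocol's visit tolerance (Days 111 to 115) falls in that gap. Unscheduled labs on Days 89 to 116 are lost from the by-visit plots as well. The trend displays in Parts A and FE then go straight from Day 85 to Day 141.

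The consequence is minor. No data leave the database, and neither the DLT endpoint nor the food-effect endpoint is touched. The conclusion assumes that the rule is programmed literally, that the printed list does begin at 12, and that the ± 2 days apply around the planned Day 113.

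**What to change.** In SAP Table 2, change the list of visit numbers to `X = 10, 12, 14, ...`. The existing formula then gives Visit 10 a planned day of 113, a window of Days 89 to 116 and analysis visit number 110. Check the numeral in the source file first.

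The cost is one number in the table, made before the by-visit laboratory outputs are programmed. It needs no extra data collection or analysis and no protocol change, since it only brings the table into line with the protocol's 4-weekly schedule.

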# 9.3 Handling of Missing Data and Imputation Rules

## Handling of missing data:

Unless otherwise specified, missing data will not be replaced.

In all participant data listings, imputed values will be presented and flagged as such.

Missing statistics, e.g., when they cannot be calculated, should be presented as "nd" (not done). For example, if n=1, the measure of variability (StDev) cannot be computed and will be presented as "nd".

Unless otherwise specified, the number of subjects counted as "missing" is the number of participants in the relevant analysis population minus the number of non-missing results for the given analysis.

Handling of missing data for PK parameter calculations is discussed under Section 16.1.

### Laboratory data outside the limit of quantitation

For laboratory assessments indicating that the sample tested below the lower limit of quantitation (LLOQ) for the analyte in question, half the lower limit of quantitation (½\*LLOQ) will be used as the analysis value. For laboratory assessments testing above the upper limit of quantitation (ULOQ), the analysis value will be imputed as {ULOQ + 1\*(the level of precision of ULOQ)}. For example, if an assessment tests at a value ">7.0", the level of precision is 0.1 and the analysis value will be 7.1. The imputed analysis values will be used in all analyses (e.g., summary statistics) and will be used for determination of toxicity grading. Listings will present the standardized unit values as provided in the raw data, indicating the assessment value was not quantifiable (e.g., ">7.0").

Partial dates will be imputed as follows:

#### Disease history

Incomplete dates for disease history (e.g., initial diagnosis date, date of documented, locally advanced, inoperable or metastatic disease diagnosis, date of response or progression to prior treatment) will be imputed as follows:

- If the day is missing, it will be imputed to the 15th day of the month.
- If both day and month are missing and the year is prior to the year of the first study treatment, the month and day will be imputed as July 1st.
- If both day and month are missing and the year is same as the year of the first study treatment, the month and day will be imputed as January 1st.
- If the date is completely missing, no imputation will be performed.

#### Adverse Events

Incomplete AE-related dates will be imputed as follows:

- If the AE onset date is missing completely, then the onset date will be replaced by the start
  of study intervention.
- If only the day part of the AE onset date is missing, but the month and year are equal to the start of study intervention, then the AE onset date will be replaced by the start of study intervention. For example, if the AE onset date is --/JAN/2015, and study intervention start date is 15/JAN/2015, then the imputed AE onset date will be 15/JAN/2015.
- If both the day and month of the AE onset date are missing but the onset year is equal to
  the start of study intervention, then the onset date will be replaced by the minimum of the
  start of study intervention and AE stop date. For example, if AE onset date is --/---/2014,
  and study intervention start date is 19/NOV/2014, then the imputed AE onset date will be
  19/NOV/2014.
- In all other cases the missing onset day or missing onset month will be replaced by 1.
- Incomplete stop date will be replaced by the last day of the month (if day is missing only),
  if not resulting in a date later than the date of subject's death. In the latter case the date of
  death will be used to impute the incomplete stop date.
- In all other cases the incomplete stop date will not be imputed.

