#### Prior/Concomitant Medication

Incomplete prior/concomitant medication dates will be imputed as follows:

- If the medication date is missing completely, then the medication date will be replaced by the start date of the first study intervention.
- If the day of medication date is missing, but the month and year are equal to the start date of
  the first study intervention, then the medication date will be replaced by the start date of the
  first study intervention. For example, if the medication start date is --/JAN/2015, and study
  intervention start date is 15/JAN/2015, then the imputed medication start date will be
  15/JAN2015.
- If both the day and month of medication start date are missing but the start year is equal to the start date of the first study intervention, then the medication date will be replaced by the start date of the first study intervention. For example, if the medication start date is --/---/2014, and study intervention start date is 19/NOV/2014, then the imputed medication start date will be 19/NOV/2014.
- In all other cases, the missing medication day or month will be replaced by 1.
- In the case that the imputed start date occurs after the medication end date, the medication end date will be used as the start date.

- Incomplete end date will be replaced by the last day of the month (if day is missing only), if not
  resulting in a date later than the date of subject's death. In the latter case, the date of death will
  be used to impute the incomplete end date.
- In all other cases, the incomplete medication end date will not be imputed.

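### Two of the four AE onset imputation rules ignore the AE stop date, so an event known to have ended before first dose is counted as treatment-emergent

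*SAP*

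**What the plan says.** The rules are in the SAP under Handling of Missing Data and Imputation Rules, Adverse Events (numbered 9.3 in the body, 9.4 in the table of contents). For an incomplete onset date they are:

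1. Onset wholly missing: "If the AE onset date is missing completely, then the onset date will be replaced by the start" of study intervention.
2. Only the day missing, month and year equal to those of first dose: "then the AE onset date will be replaced by the start of study intervention".
3. Day and month missing, year equal to that of first dose: "then the onset date will be replaced by the minimum of the" "start of study intervention and AE stop date".
4. Everything else: "In all other cases the missing onset day or missing onset month will be replaced by 1".

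A stop date that lacks only its day is moved to the end of the month, capped at death. Otherwise, "In all other cases the incomplete stop date will not be imputed".

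The next subsection, on prior and concomitant medication, adds a general safeguard. It begins "In the case that the imputed start date occurs after the medication end date" and resets the start to that end date. The rule for subsequent anti-cancer therapy also checks the end date. The AE list has no such general line.

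**The concern.** Rules 1 and 2 can contradict data already recorded. Protocol 8.3.1 starts AE collection at informed consent, and Protocol 4.1.1.1 allows up to 28 days of screening in Parts A and FE and 35 in Part B. An AE can therefore begin and resolve before Day 1 and still be on the AE page. SAP 15.1 makes an event treatment-emergent by its onset date, and SAP 9.1 starts the on-treatment period at first dose. When onset is imputed to first dose, such an event enters the TEAE tables even though its own stop date shows that it was over before any study intervention was given. Rule 1, where least is known about onset, has less protection than rule 3.

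**Working it through.** **Inputs.** The four onset rules above; TEAE = imputed onset on or after first dose (SAP 15.1 with the on-treatment definition in SAP 9.1); duration = stop − onset + 1 (SAP 9.1); screening windows of 28 and 35 days (Protocol 4.1.1.1).

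**The SAP's own examples.** Neither has a stop date. Onset --/JAN/2015 with first dose 15/JAN/2015 falls under rule 2 and gives 15/JAN/2015. Onset --/---/2014 with first dose 19/NOV/2014 falls under rule 3 and gives 19/NOV/2014. Both match the SAP.

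**The same rules with a stop date before first dose.**

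| Rule | Recorded onset | Stop | First dose | Imputed onset | TEAE? | Duration (days) |
|---|---|---|---|---|---|---|
| 1 | missing | 10/JAN/2015 | 15/JAN/2015 | 15/JAN/2015 | yes | 10 − 15 + 1 = −4 |
| 2 | --/JAN/2015 | 10/JAN/2015 | 15/JAN/2015 | 15/JAN/2015 | yes | 10 − 15 + 1 = −4 |
| 3 | --/---/2014 | 10/NOV/2014 | 19/NOV/2014 | 10/NOV/2014 | no | 10 − 10 + 1 = 1 |
| 4 | --/DEC/2014 | 10/JAN/2015 | 15/JAN/2015 | 01/DEC/2014 | no | 41 |

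**Is this peculiar to the example?** I applied the rules to every first-dose date in 2020 (an arbitrary year of 366 days) and every stop date in the screening window before it. Each onset was masked in three ways: wholly, day only, and day and month. The table shows how many cases end with onset after stop and false TEAE status.

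| Rule | 28-day window | 35-day window |
|---|---|---|
| 1 | 10248 of 10248 (366 × 28) | 12810 of 12810 (366 × 35) |
| 2 | 5376 of 5376 | 5401 of 5401 |
| 3 | 0 of 9842 | 0 of 12180 |
| 4 | 0 of 5278 | 0 of 8039 |

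These counts show that rules 1 and 2 fail whenever a pre-dose stop date is known, and that rules 3 and 4 do not. They say nothing about how often such records occur.

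**Size of one misclassified event.** Protocol 6.6.4 expects 3 to 6 participants per dose level: 1/6 = 17% and 1/3 = 33%. This is for one preferred-term row at one dose level. It assumes that the participant has no genuine on-treatment event of that term, since SAP 15.1.1 counts each participant once.

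**With the stop date respected.** Rules 1 and 2 in the first table both give onset 10/JAN/2015, not a TEAE, duration 1 day. The tested results under rules 3 and 4 and both SAP examples are unchanged.

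**The case against.** The best defence is that imputing to first dose is a deliberately cautious convention: when timing is unknown, count the event as on treatment. That stands when the stop date is unknown or falls on or after first dose. It does not stand when a recorded stop date settles the question, and rule 3 shows that the SAP accepts this.

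A second defence is that few such records will survive. Protocol Appendix 4 asks for onset and resolution dates for each AE and excludes conditions already present at the initial visit that do not worsen. SAP section 6 relies on cleaned data and a review meeting before lock, and imputed values are flagged in listings. All of this lowers the frequency and makes the anomaly visible in a listing, but it does not correct a table.

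Four stronger readings are tempting, and the documents do not support them:

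- **That incomplete onset dates in general are mishandled.** Rule 3 already takes the minimum with the stop date, and rule 4 does not use first dose.
- **That pre-treatment events will appear as treatment-related.** Relatedness is the investigator's report for each component (SAP 15.1), not a product of the imputed date. An affected event reaches the related-TEAE tables only if relatedness was left blank, which the SAP counts as related, or was recorded as related.
- **That negative durations distort results.** SAP 15.1 and 15.2 plan counts, percentages, timing of the first infusion reaction, and listings. No planned summary uses AE duration.
- **That the primary endpoint is at risk.** A DLT must be related to a study intervention and confirmed by the SMC (Protocol 6.6.3), and the investigator identifies it (SAP 15.2.1). An imputed date alone does not create one.

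**Conclusion.** The point holds for two cases only: onset wholly missing, and day alone missing in the month and year of first dose. In both, an AE with a known stop date before first dose is always given an onset after its stop and counted as a TEAE. The consequence is limited to TEAE tables and listings, at 17 to 33 percentage points on a single row per event under the conditions above.

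The number of such events is not in the documents. I assume it is small, because it needs an AE that arose after consent, ended before dosing, and has an incomplete onset but a usable stop date. This is a minor correction, worth making because the rule as written gives a wrong answer and the remedy is already in the adjacent text.

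**What to change.** In rules 1 and 2, replace the imputed value with the minimum of the "start of study intervention and AE stop date", as rule 3 does. Alternatively, add one line after the AE onset rules that mirrors the medication rule and resets any imputed onset falling after the stop date to the stop date. Either version should say that first dose is used when no stop date is available. The cost is two phrases or one sentence in the SAP and the matching line of code. No new data are needed.
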